### Part II: Data and Safety Monitoring Board or Committee

- *When appropriate, attach a description of the DSMB.*

- *Provide the number of members and area of professional expertise.*
- *Provide confirmation that the members of the board are all independent of the study.*

Given that study activities involve no more than risks encountered in daily life (increased time spent walking by healthy, working individuals), the study has not convened a DSMB.

## 16. WITHDRAWAL OF SUBJECTS

- *Describe anticipated circumstances under which subjects will be withdrawn from the research without their consent*
- *Describe procedures for orderly termination*
- *Describe procedures that will be followed when subjects withdraw from the research, including partial withdrawal from procedures with continued data collection.*

Circumstances under which participants will be withdrawn from the research without their consent include failure to maintain protocol adherence and repeated failure to complete the assigned BCT intervention.

Potential participants will be notified of the possibility of being removed from the study before or during the BCT intervention phase due to adherence issues in the informed consent. Participants who fail to maintain minimum adherence during baseline will be notified by the research team after 10 days of baseline participation.

Participants who fail to maintain protocol adherence or who deviate from the protocol will be contacted by a member of the study team with a reminder of the study protocol, and warning that this may impact their continued study eligibility. Once a protocol deviation has been repeatedly recorded, the Principal Investigator will determine the participant's continued eligibility in the study, with consultation of the Safety Officer if needed. If it is determined that the participant will be withdrawn from the study, the participant will be notified by the research team via email and phone call. The participant will stop receiving notifications and survey prompts, and will be sent instructions to un-link their Fitbit device. The participant will be able to keep their Fitbit device but will be required to return their eCAP smart pill bottle.

Participants may withdraw from participation in the research at any time. Given the non-invasive nature of study-specific monitoring, there are no significant anticipated direct adverse effects related to withdrawal. Participants may easily elect to withdraw by emailing Research personnel directly at:

[name]  
 [name]  
 [name]  
[[contact]](mailto:[contact])

If a participant withdraws from the study, previously collected data will not be deleted. However, no new information will be collected from a participant after he/she has withdrawn from the study. We will clarify how to transfer the Fitbit

to a personal account and will ask participants to complete a satisfaction survey at the time of their withdrawal (as proposed for all participants who complete the research) to tell us about their experience in the study. The participant will be sent an electronic survey including questions regarding their experience during the study, or will be contacted by phone or teleconference if they do not complete the electronic survey. Completion of this survey is voluntary and will help us design better research in the future.

Participants will be considered to be “active” until we are notified of their request to terminate participation.

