*Environmental context and resources* is defined as aspects of a person’s situation or environment that discourage or encourage the behavior. This MoA will be assessed using a checklist of 7 potential barriers to physical activity identified by Steinhart and colleagues [29] Barriers are coded on a 1 (Not often at all) to 5 (Very often) scale, and averaged to create a total score, with higher scores indicating that the listed barriers had greater effects on walking.

Following completion of the 2-week run-in period, participants will receive a variable duration BCT intervention, and the length of the intervention is determined by utilization of the modified TiTE-CRM design. During the BCT intervention, participants will receive 5 daily BCTs via text message. Content of the text message will be specific for each BCT (e.g. a Goal Setting text message will encourage participants to develop a walking goal for the day). Initially, 3 participants will be treated at a moderate dose level, which is five weeks of the multi-BCT intervention to increase PA. Based on the calculated MED for the first cohort, subsequent cohorts will be administered a longer or shorter dose of the intervention. The BCT dose for each cohort will be determined by the study statistician based on the proportion of individuals in the prior cohort exhibiting the target behavior (in this case, a 2,000 step per day increase between baseline and follow-up periods). As the MED involves comparing PA levels between the run-in and follow-up periods, participants will not be assigned to subsequent cohorts unless all of the participants in the prior cohort have completed some of the intervention period. The treatment response for the prior cohort will be used to guide the dose administered to the subsequent cohort using modified TiTE-CRM methodology.

Following the completion of the intervention, all cohorts will be assessed for a 2 week follow-up period. Follow-up consists of wearing the activity monitor continuously, and use of electronic pill bottle to assess adherence. No interventions will be delivered during this period. At the end of the study, participants will be asked to complete the same questionnaire completed during baseline and the intervention phase as well as a satisfaction survey regarding the BCT intervention. Participants will also be reminded/instructed to return their eCAP smart pill bottle to the study team via addressed packaging included in their study materials.

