## 12. STATISTICAL ANALYSIS

- *Describe how your data will be used to test the hypotheses.*
- *State clearly what variables will be tested and what statistical tests will be used.*
- *Include sample size calculations.*
- *If this is a pilot study, state which variables will be examined for hypothesis generation in later studies.*

Analysis for the Primary Aim: The minimum effective dose (MED) will be defined as the smallest BCT dose duration associated with a successful PA increase (defined as an average increase of 2,000 steps per day) between the 2-week run-in and 2-week follow-up periods in at least 80% of participants. The MED will be estimated based on the modified TiTE-CRM, which is an adaptive model-based, dose-finding design for estimating the maximum tolerated dose in pharmacologic agents. In this study, we will adapt the TiTE-CRM for the purpose of MED estimation. Briefly, the TiTE-CRM operates as follows during a study. Participants will be enrolled in cohorts of 3. The first cohort will be given a BCT intervention with a duration of 5 weeks. Subsequent cohorts will be given a BCT intervention duration (from 1-week to 10-week) based on the updated MED estimate according to the modified TiTE-CRM model and data from the previously enrolled participants. The process will continue until we reach a total of 42 participants (14 cohorts) randomized to the intervention. Once the study has completed enrollment, we will identify which dose of the BCT intervention (in weeks) is associated with  $\geq 80\%$  of participants achieving the goal of an average of 2,000 steps per day increase between the baseline and follow-up periods. Means and standard deviations of step scores for baseline versus behavioral change strategy treatment period will be visualized using a column graph. The statistical significance of differences will be adjusted for time interval. The effects of treatment on number of steps will be assessed using generalized linear mixed models (GLMM). This model will account for possible autocorrelation and linear trends between steps across time.

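### Participants removed by the investigator are told to un-link the Fitbit, so the follow-up steps that decide the primary outcome are lost when they could be collected passively

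*Combined protocol and SAP*

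**What the plan says.** Section 16 of the combined protocol and SAP gives the grounds for removal by the investigator: "withdrawn from the research without their consent include failure to maintain protocol adherence and repeated failure to complete the assigned BCT intervention". The consent form is to warn of "being removed from the study before or during the BCT intervention phase due to adherence issues", so removal can come after a duration has been assigned. Before it happens there is a reminder, a warning and a decision by the Principal Investigator on repeated deviations. After it, "The participant will stop receiving notifications and survey prompts, and will be sent instructions to un-link their Fitbit device". A later paragraph of the section, which opens with voluntary withdrawal, says that "no new information will be collected from a participant after he/she has withdrawn from the study".

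The template instruction at the head of Section 16 asks for withdrawal procedures "including partial withdrawal from procedures with continued data collection". The section gives no such route for step data; its only contact after withdrawal is a voluntary satisfaction survey.

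The primary outcome depends on those steps. Section 2 defines the change in activity as follow-up minus run-in. Section 12 defines the MED by a 2,000-step increase "between the 2-week run-in and 2-week follow-up periods in at least 80% of participants". Section 11 has the statistician set each cohort's duration "based on the proportion of individuals in the prior cohort exhibiting the target behavior". Sections 11 and 12 do not say how a removed participant enters either calculation.

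**The concern.** This is a stated procedure that discards the primary outcome, not only a missing detail. Steps are recorded passively, the removed participant keeps the device, and the data are lost only because the account is un-linked.

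The loss may be selective. People removed for not completing the intervention could plausibly be less likely to reach the step goal. If they are then left out, the remaining participants look more successful than all those assigned that duration, and the design moves to a shorter duration than the one that truly reaches 80%. With cohorts of three, one removal can matter during the trial as well as in the final estimate.

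**Working it through.** **Inputs from the plan.** 42 participants in 14 cohorts of 3; durations of 1 to 10 weeks; start at 5 weeks; target 80%; acceptable band 75-85%; 60% probability of correct selection (PCS); logistic slope 0.69, that is, an odds ratio of 2 (Section 12).

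**Assumptions.** The slope is ln 2 per week (Section 12 gives no unit). The model is a one-parameter power CRM on non-success with target 0.20, normal prior variance 1.34 and half-width 0.05. Updates use complete outcomes, not the planned time-to-event weighting, whose weights are not given. No skipping rule applies. The true MED lies at weeks 3 to 8, and results are averaged over these. Let f be the share of non-successes removed, s the share of successes removed, and r the share of removed participants whose follow-up steps are recovered. None of f, s or r is in the documents.

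**Step 1: the plan's own figure.** With every outcome observed, simulated PCS is 0.61 and true success at the selected duration is 0.80. A separate coding gave 0.595 to 0.639 across half-widths 0.03 to 0.06. The stated 60% is reproduced, on the footing that no outcome is missing.

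**Step 2: arithmetic when removed participants are dropped.** Observed odds of success = true odds × (1 − s)/(1 − f). A duration that appears to reach 0.80 (odds 4) therefore has true odds 4(1 − f)/(1 − s).

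- f = 0.10, s = 0: odds 3.6, true success 3.6/4.6 = 0.783
- f = 0.15, s = 0: odds 3.4, true success 3.4/4.4 = 0.773
- f = 0.25, s = 0: odds 3.0, true success 3/4 = 0.750
- f = 0.50, s = 0: odds 2.0, true success 2/3 = 0.667
- f = s: odds 4, true success 0.800, no shift

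**Step 3: simulation, removed participants dropped, none recovered.**

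| f | s | PCS | True success | Mean error (weeks) |
|---|---|---|---|---|
| 0 | 0 | 0.61 | 0.80 | +0.11 |
| 0.10 | 0 | 0.61 | 0.79 | −0.04 |
| 0.15 | 0 | 0.59 | 0.78 | −0.12 |
| 0.25 | 0 | 0.53 | 0.755 | −0.30 |
| 0.50 | 0 | 0.25 | 0.675 | −0.89 |
| 0.10 | 0.10 | 0.59 | 0.80 | n/a |
| 0.25 | 0.25 | 0.55 | 0.80 | n/a |

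(n/a: not tabulated; mean true success is unchanged.) With s = 0, the rows f = 0.10, 0.15, 0.25 and 0.50 correspond to about 1.0, 1.5, 2.7 and 7.0 of the 42 participants.

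If the odds ratio of 2 applies per 2 weeks, complete-data PCS is only 0.37, which does not match the plan's 60%. True success at f = 0.25 is then 0.748, so that loss depends little on the slope unit.

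**Step 4: one cohort.** With one removal and two successes, the proportion is 2/3 = 67% if the removed person counts as non-success and 2/2 = 100% if dropped. These fall on opposite sides of 80%.

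**Step 5: what continued collection could recover (f = 0.25).** With no recovery and removed participants dropped, PCS is 0.53, 0.55 and 0.56 for s = 0, 0.05 and 0.10. With r = 0.70 and only the remainder dropped, it is about 0.60 to 0.62 and the error is close to zero. At s = 0.10, true success moves from 0.77 to 0.80. This assumes that removal does not change later steps.

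**Step 6: scoring the missing as non-success instead.** An apparent 0.80 then needs true success 0.80/(1 − s): 0.842 at s = 0.05 and 0.889 at s = 0.10. The latter has odds 8 instead of 4, exactly one week longer at ln 2 per week. At f = 0.25 and s = 0.10, simulated PCS is 0.23 and true success 0.88. With 70% recovery, PCS is 0.51, still below the 0.56 from dropping with no recovery. If s = 0, this scoring causes no bias.

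**The case against.** **The numbers affected may be few.** Run-in screening and the reminder-and-warning steps come before removal, this is a pilot, and at 10-15% of non-successes the effect is small. This stands, and it limits the size of the point.

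**The simulation is not the planned method.** The plan uses a modified TiTE-CRM, which can weight incomplete follow-up. This stands for the exact figures. It does not close the gap, because the documents give no weights and the only partial-data statement, in Section 11, concerns how far a cohort must have progressed before the next is assigned.

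**Continued collection may recover little.** Protocol adherence may include wearing the device, and non-wearers supply no steps. Also, "participants will receive 5 daily BCTs via text message", and messages stop on removal, so former successes may lapse. With f = 0.50, s = 0.10, r = 0.70 and the rest dropped, PCS is 0.595 without lapse and 0.398 (error +0.65 weeks) if removed successes lapse, judged against the MED for people not removed. Both limits stand.

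**The no-further-collection sentence follows the voluntary-withdrawal text.** True, but its wording covers any withdrawal, and un-linking ends capture anyway.

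**Stronger readings that the documents do not support.** A reader might infer that the MED will be biased short. Adherence is not defined as walking, so a link between removal and missing the step goal is an assumption. A reader might also take Section 11's proportion of the prior cohort to mean that a removed participant counts as a non-success, or conclude that this should be the primary rule. The text does not address an unobserved outcome, and Step 6 shows that this scoring can do more harm than dropping. Nothing here disputes the 60% PCS figure.

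**Conclusion.** The point holds as a cheap improvement. It follows from the text alone that the procedure for investigator removal leaves the primary outcome unobserved after assignment. Whether this biases the MED depends on who is removed and how they are scored. If removed participants are dropped, the bias is towards too short a duration only when non-successes are removed more often than successes. It is negligible at about 10% of non-successes, and at about 25% it brings true success to the lower edge of the plan's 75-85% band. Confidence is medium, because removal rates, recovery rates, CRM settings and the slope unit are all assumed. The absence of a scoring rule is, by itself, a matter of missing detail and of trade-offs; the documents do not settle one rule as correct.

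**What to change.** Leave the removal criteria unchanged.

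- **Section 16.** For participants removed by the investigator after assignment, keep the Fitbit study account linked and collect steps passively through the 2-week follow-up scheduled for their assigned duration, unless they decline. Send the un-link instruction after that. Limit the no-further-collection sentence to those who withdraw themselves or decline, with matching consent text.
- **Section 12.** Analyse everyone assigned a duration at that duration, using observed follow-up steps whether or not the intervention was completed. Report the number of still-missing outcomes per duration, and the MED with these dropped, all set to non-success and all set to success. Do not prescribe non-success scoring as the primary rule.

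**Cost.** A consent and IRB change, including the question of collecting data by default from people removed without their consent. Little new infrastructure is needed: removed participants already keep the device, and Section 14 already has the coordinator choose the date on which Fitabase tracking ends. There is no gain from people who stop wearing the device. If removed successes lapse once messages stop, the recovered steps show the effect of assigning a duration, not of completing it, and the report should say so.

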## 17. RISKS TO SUBJECTS

- *Describe any potential risks and discomforts to the subject (physical, psychological, social, legal, or other) and assess their likelihood and seriousness and whether side effects are reversible. Where appropriate, describe alternative treatments and procedures that might be advantageous to the subjects.*
- *Include risks to others, like sexual partners (if appropriate)*
- *Discuss why the risks to subjects are reasonable in relation to the anticipated benefits and in relation to the importance of the knowledge that may reasonably be expected to results*
- *Describe the procedures for protecting against or minimizing any potential risks, including risks to confidentiality, and assess their likely effectiveness.*

This study poses low risk of physical harm to subjects.

One risk of taking part in this study is the possibility of a loss of confidentiality or privacy. The study team plans to protect privacy by only sharing necessary information about participants to those outlined in the consent form. All subjects will be informed that their responses are confidential and that they may refuse to participate in the project or withdraw at any time without explanation, and that such action will not affect their future interactions with their health care providers, employment, educational studies, or the research study. The risk of loss of confidentiality will be minimized by securely storing data including PHI in a Northwell-approved database and minimizing the use of PHI.

There is no additional risk with using a Fitbit activity monitor for research as compared to using the device as a consumer, including mild skin irritation (i.e. contact dermatitis) which occurs among a small proportion of users. Participants will be instructed via the consent form on methods to reduce irritation (i.e. keep the band clean and dry) and that they can remove the band for a short period of time.

There are no known risks associated with utilization of the BCTs employed in this intervention. It is possible that messages prompting physical activity may cause mild stress in participants who are ambivalent about increasing their step count. Increasing step count by 2,000 steps per day in ambulatory persons without mobility impairments or safety limitations represents no more than minimal risk. Mild symptoms of increased activity such as fatigue or muscle soreness may be experienced.

There are no known risks to utilizing eCAP smart pill bottle. The vial smart cap meets all federal standards for safety (childproof). No patient information or identifying data is stored on the device. There is no GPS tracking from the eCAP device.

The proposed questionnaires are not anticipated to pose risk to the participants. Participants will receive text message notifications with a secure link to a survey that can be accessed via a smartphone. All survey responses will be directly entered by participants in an electronic format (secure, HIPAA compliant RedCap database).

#### **18. RESEARCH RELATED HARM/INJURY**

- *Describe the availability of medical or psychological resources that subjects might need as a result of anticipated problems that may be known to be associated with the research.*
- *If the research is greater than minimal risk, explain any medical treatments that are available if research-related injury occurs, who will provide it, what will be provided, and who will pay for it.*

Research-related injuries are not expected for this no greater than minimal risk project.

#### **19. POTENTIAL BENEFIT TO SUBJECTS**

- *Explain what benefits might be derived from participation in the study, noting in particular the benefit over standard treatment (e.g. a once-a-day administration instead of four times a day, an oral formulation over an IV administration).*
- *Also state if there are no known benefits to subjects, but detail the value of knowledge to be gained*

Participating could improve physical activity and subsequently reduce cardiovascular risk. In addition, the information collected from participant involvement will inform the development of future BCTs to help other research participants, and eventually patients, discover which behavioral treatment options are best for them as an individual.

## 20. PROVISIONS TO PROTECT PRIVACY INTERESTS OF SUBJECTS

- *Describe the methods used to identify potential research subjects, obtain consent and gather information about subjects to ensure that their privacy is not invaded.*
- *In addition consider privacy protections that may be needed due to communications with subjects (such as phone messages or mail).*

The study will be advertised to potential participants via established Northwell communication channels, including via NWH secure email and secure communication with Quantitative Intelligence (QI). Inter-departmental support has been shown across Northwell to assist the researchers in meeting recruitment goals. Their extensive electronic communication system will allow for the rapid delivery of recruitment materials directly to potentially-eligible participants.

Recruitment links will lead to a study web page asking potential participants to sign authorization to undergo brief screening to assess if they are eligible for participation and to provide demographic information needed to comply with NIA regulations. Participants who authorize the study team will be provided with more information about study requirements, eligibility, and who to contact for more information. Interested individuals will be asked to sign consent via a 21 CFR Part 11 and HIPAA compliant Northwell Health approved electronic platform. Individuals may call the research team at any time to ask questions prior to signing consent. Should this occur, research personnel will ensure that the individual is in a private location for open conversation to protect the privacy interests of the individual. All study-related communications will be delivered via a secure, NWH email or via the NWH approved e-platform.

